3.2. Previous Clinical Studies Leading Up to and Supporting the Proposed Research

Inoue et al has reported on the safety and feasibility of percutaneous cryoablation for lung tumors. This study included 396 lung tumors in 117 (104 with metastatic disease) consecutive patients conducted in 193 cryoablation sessions. All patients tolerated the procedure well. The mean follow up period was 899± 778 days. Adverse events were categorized using the CTCAE system. Pneumothorax was the most common complication observed in 61.7% of the treatment sessions. Of these, 10.9% of the cases required chest tube insertion, comparable to that associated with RF ablation. Delayed and recurrent pneumothorax each occurred in 30 of the treatment sessions, resulting in 17 chest tube insertions. Risk factors predictive of pneumothorax were male sex, and greater number of cryoneedles. The authors theorize the higher pneumothorax rate may be related to the number of cryoneedles used, thicker modified coaxial system, and the modality used to detect pneumothorax. Pleural effusion occurred in 136 treatment sessions and required no additional treatment. No CTCAE grade 4 or 5 events were observed. Three grade 3 complications were noted; one in which an empyema required fenestration and 2 cases of pneumothorax which required pleurodesis. Inoue et al concluded that percutaneous cryoablation is minimally invasive and associated with improved safety.³²

Yamouchi et al reported the use of percutaneous cryoablation for pulmonary metastases from colorectal cancer on 24 patients for 55 tumors during 30 treatment sessions. Follow up scans were performed every 3-4 months after treatment. Pneumothorax was reported in 19 sessions with only 1 session requiring insertion of a chest tube. A small amount of pleural effusion occurred in 21 sessions, none of which required a chest tube. The 1- and 3-year local progression free intervals were 90.8% and 59%, respectively. The 1- and 3-year overall survival rates were 91% and 59.6%, respectively.³³

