10.5.5. Other Data Assessments

Technically successful treatment definition

A technically successful treatment will be defined by the presence of an ablation zone, ground glass opacity, or frank consolidation encompassing the targeted index tumor(s) no later than the 1 month follow up visit after the cryoablation procedure. Technical success will be analyzed on a per tumor basis.

Disease recurrence or progression definitions

The reference date for disease progression evaluation will be associated with the initial (first) cryoablation procedure done per study protocol. In the event of multiple cryoablation procedure dates, such as with bilateral lesions or staged treatments, the date of reference for disease progression evaluation will be the initial (first of n) cryoablation procedure.

- **Local disease progression** will be determined locally by evidence of local tumor failure.
- **Lung-disease-specific survival rate** is defined as the time in days from the first cryoablation procedure to death and **a)** the date of metastatic lung tumor progression (new lung tumors or local tumor failure of the index tumor), **b)** the date of death with local control of the index tumor, or **c)** the date of last follow up in patients who were still alive with local tumor control of the index tumor. Patients who are alive will be censored at the date of their last visit. Patients who have died from causes other than local failure of the index tumor will be censored at the time of death. Lung disease-specific survival rates will be summarized by using Kaplan-Meier methodology.
- **Overall survival rate** is defined as the time in days from the first cryoablation procedure to death. Patients who are alive will be censored at the date of the last visit. Overall survival rates will be summarized by using Kaplan-Meier methodology.
- **Time to metastatic lung disease progression beyond the index tumor** is defined as the time in days from the first cryoablation procedure to metastatic disease beyond the index tumor site. Patients without metastatic lung disease progression will be censored at the date of their last visit or their date of death (due to any cause). Metastatic progression free survival rates will be summarized by using Kaplan-Meier methodology.

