Galil Medical**CUC13-LNG079-02: Multi-center Study of Metastatic Lung Tumors Targeted by Interventional Cryoablation Evaluation (SOLSTICE)****Statistical Analysis Plan (SAP)****Table of Contents**

Protocol Summary	2
Objective	2
Study Design.....	2
Sample Size Justification.....	2
General Analysis Methods	3
Analysis Populations	3
Efficacy Endpoint Analysis	4
Efficacy Endpoint.....	4
Analysis Methods	4
Safety Endpoint Analysis.....	4
Safety Endpoint	4
Analysis Methods	4
Supportive Endpoint Analyses	5
Tumor control (patient level & weighted average response).....	5
Tumor control (pulmonary metastatic disease).....	5
Tumor control (additional cryoablation).....	5
Technically successful treatment	5
Disease recurrence or progression	5
Intra-procedural data	6
Physical performance and quality of life.....	6
Additional Data Summaries	7
Subject Disposition.....	7
Randomization and Blinding	8
Handling of Missing Data	8
Subset Analyses	8
Poolability Analyses	8
Interim Reporting.....	9
Statistical Software	9
Version, Revision History, and Approvals	10

Current Version	10
Revision History.....	10
Approvals.....	11

Protocol Summary

Objective

The objective of this study is to assess the safety and to demonstrate efficacy of cryoablation in local tumor control for tumors ≤ 3.5 cm in patients with pulmonary metastatic disease.

Study Design

This is a Phase II multicenter, prospective, single arm. Target inclusion for this study is 226 lesions. It is estimated this study will enroll 150 patients in order to achieve the target lesion goal. Patients enrolled will undergo cryoablation of at least 1 metastatic pulmonary tumor via a Galil Medical cryoablation system using Galil Medical cryoablation needles.

Patients will be screened within 8 weeks of the cryoablation procedure. After the cryoablation procedure visit date, protocol directed follow-up visits will consist of within 1 Week of the cryoablation procedure and then 1, 3, 6, 12, 18, and 24 months post cryoablation procedure.

Sample Size Justification

This is a prospective, single-arm study designed to determine the safety and efficacy of Galil Medical's Cryoablation System and needles in cryoablation of metastatic lung tumors.

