- **Time to metastatic lung disease progression beyond the index tumor** is defined as the time in days from the first cryoablation procedure to metastatic disease beyond the index tumor site. Patients without metastatic lung disease progression will be censored at the date of their last visit or their date of death (due to any cause). Metastatic progression free survival rates will be summarized by using Kaplan-Meier methodology.
- **Time to overall cancer progression** is defined as the time in days from the first cryoablation procedure to cancer progression (i.e., any location of active cancer disease). Patients without cancer progression will be censored at the date of their last visit or their date of death (due to any cause). Overall cancer progression free survival rates will be summarized by using Kaplan-Meier methodology.
- **Time to untreatable metastatic lung disease control with cryoablation** is defined as the time in days from the first cryoablation procedure to the time when the metastatic lung disease cannot be treated with cryoablation. Overall time to untreatable metastatic lung disease progression rates will be summarized by using Kaplan-Meier methodology.
- **Time to untreatable metastatic lung disease control with focal therapy** is defined as the time in days from the first cryoablation procedure to the time when the metastatic lung disease cannot be treated by focal (e.g., ablation, surgery, SBRT) intervention for control of metastatic lung disease. Overall time to untreatable metastatic lung disease progression rates will be summarized by using Kaplan-Meier methodology.

Intra-procedural data

Initial cryoablation procedure information including the type of procedure, tumor size and number, cryoablation needle type and the number of each type of needle used, freeze and thaw times, procedure times, and anesthesia type will be summarized using descriptive statistics.

Physical performance and quality of life

Physical performance (KPS) and quality of life (SF-12) assessments will be made by examining the change in the baseline scores to those reported post-operatively and at follow-up visits. The KPS scale and each of the eight SF-12 domains will be summarized at each time point by descriptive statistics. Percent change from baseline for each measure will also be summarized by descriptive statistics.

Additional Data Summaries

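### Two progression outcomes censor deaths, use Kaplan-Meier and are labelled progression-free survival, so the curves estimate neither the risk of progression nor progression-free survival.

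*SAP*

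**What the plan says.** Under Disease recurrence or progression, the SAP defines two patient-level times from the first cryoablation: to metastatic lung disease outside the index tumor, and to cancer progression at any site. For the first, "Patients without metastatic lung disease progression will be censored at the date of their last visit or their date of death". For the second, "Patients without cancer progression will be censored at the date of their last visit or their date of death". In both cases the death may be from any cause.

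The SAP then names the estimator and the label: "Metastatic progression free survival rates will be summarized by using Kaplan-Meier methodology" and "Overall cancer progression free survival rates will be summarized by using Kaplan-Meier methodology". Protocol 10.5.5 has the same censoring rule, estimator and label.

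Neither document plans a competing-risk estimator. Overall survival is analysed separately, also by Kaplan-Meier, with death as the event. The two progression outcomes are listed in Protocol 5.3 as other data and in the SAP under Supportive Endpoint Analyses, with no hypothesis test.

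**The concern.** A patient who dies without progression can no longer progress. Kaplan-Meier with that death censored treats the patient as still at risk, at the rate seen in survivors. So 1-KM exceeds the proportion of patients who actually progress whenever anyone dies progression-free.

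The label does not repair this. Progression-free survival counts progression or death, whichever comes first. A curve in which deaths are censored is too high for that quantity. The same curve is therefore wrong under both natural readings: it makes progression look too frequent if read as time to progression, and outcome look too good if read as progression-free survival.

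This is a single-arm study, so there is no control arm that shares the distortion, and readers will tend to take such curves as absolute risks. Deaths before progression are plausible: patients have stage 4 disease, KPS may be as low as 60, and life expectancy need only exceed 3 months (Protocol 6.2).

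**Working it through.** **Figures in the plan.** The documents give no expected rate, precision or death-before-progression rate for these outcomes, so there is no stated figure to reproduce. Neither document fixes a reporting time for them; I use 24 months, the last scheduled visit ("then 1, 3, 6, 12, 18, and 24 months post cryoablation procedure").

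**Inputs from the documents.**
- Patients: "It is estimated this study will enroll 150 patients".
- Survival, from the colorectal-metastasis cryoablation series of 24 patients in Protocol 3.2: "The 1- and 3-year overall survival rates were 91% and 59.6%, respectively".

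**Assumptions, not in the documents.**
- Progression (1-KM) of 30%, 50% or 70% at 24 months, at a constant hazard.
- Death hazard before progression equal to the full cited hazard, or to a half, a quarter or a tenth of it.
- Independent hazards.
- Withdrawal of 5% per year (used for the standard error only).

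**Step 1, death hazard.** Year 1: -ln(0.91) = 0.0943 per year. Years 2 and 3: -ln(0.596/0.91)/2 = 0.2116 per year. Survival at 24 months: 0.91 × exp(-0.2116) = 73.6%, so about 26% are dead. This includes deaths after progression, so it is an upper bound on the competing deaths if mortality here is like that in the series.

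**Step 2, formulas.** Let λ be the progression hazard, and let a₁ and a₂ be the pre-progression death hazards in years 1 and 2.
- 1-KM = 1 - exp(-2λ).
- Cumulative incidence = λ/(λ+a₁) × (1-S₁) + S₁ × λ/(λ+a₂) × (1-exp(-(λ+a₂))), with S₁ = exp(-(λ+a₁)).
- Progression-free survival = exp(-2λ) × exp(-(a₁+a₂)).

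**Step 3, worked case: 50% progression, full death hazard.** λ = ln(2)/2 = 0.3466 and S₁ = exp(-0.4409) = 0.6435.
- Year 1: 0.3466/0.4409 × 0.3565 = 0.280.
- Year 2: 0.6435 × 0.3466/0.5582 × 0.4278 = 0.171.
- Cumulative incidence is 45.1%, against 1-KM of 50%: 4.9 points too high.
- Progression-free survival is 0.50 × 0.736 = 36.8%, against a reported 50%.

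**Step 4, range for 1-KM read as the probability of progression.** Entries are the overstatement in points at 24 months. In brackets is its ratio to the standard error (SE) of 1-KM with 150 patients, from the integrated Greenwood formula (SE about 3.9 to 4.5 points).

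| Share of cited death hazard before progression | 30% progress | 50% progress | 70% progress |
|---|---|---|---|
| Full | 3.1 (0.8) | 4.9 (1.1) | 6.1 (1.5) |
| Half | 1.6 (0.4) | 2.5 (0.6) | 3.2 (0.8) |
| Quarter | 0.8 (0.2) | 1.3 (0.3) | 1.6 (0.4) |
| Tenth | 0.3 (0.1) | 0.5 (0.1) | 0.7 (0.2) |

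**Step 5, the same curve read as progression-free survival, at 50% progression.** The reported value would be 50%. With a₁+a₂ = 0.3059 at the full hazard, the value with death as an event is:
- full: 0.50 × exp(-0.3059) = 36.8%;
- half: 0.50 × exp(-0.1530) = 42.9%;
- quarter: 0.50 × exp(-0.0765) = 46.3%;
- tenth: 0.50 × exp(-0.0306) = 48.5%.

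At 50% progression, this gap is larger than the overstatement in Step 4 at every share.

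**The case against.** The best case for the plan has four parts.

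**The size is not known.** A reader might infer that 24-month progression is overstated by half to one standard error or more. The documents do not support that as a general statement. The cited survival is all-cause, from one small series, and includes deaths after progression, which do not compete. For progression at any site in particular, many patients may progress before they die. At a quarter or a tenth of the death hazard, every entry in the table is below half a standard error. This part stands, and the size must be given as a conditional range.

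**The only documented event rates belong to another outcome.** The same cited series gives local progression-free figures of 90.8% and 59% at 1 and 3 years. With the full death hazard these yield a 24-month 1-KM of 26.8% against a cumulative incidence of 23.3%. But that is local progression. There the SAP names Kaplan-Meier but no rule for censoring deaths, and Protocol 10.5.5 names no estimator. The example cannot size the two outcomes at issue. This also stands.

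**The plan promises progression-free survival, not a probability of progression.** This is true of the label, but it does not rescue the analysis. Under that label deaths must be events, and the curve is then too high. The objection changes the direction of the error but does not remove it.

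**The outcomes are supportive.** They carry no test or threshold, and overall survival and the number of deaths are reported separately. This stands and limits the importance. It is not a reason to leave a curve that matches neither its name nor its label.

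**Conclusion.** The point holds as an inconsistency between the death rule, the estimator and the label in both documents. Whenever patients die progression-free, 1-KM overstates the probability of progression, and the Kaplan-Meier curve overstates progression-free survival.

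The direction under each reading is certain; the size is not. It runs from 0.3 to 6.1 points for the probability of progression, over 30% to 70% progression and a tenth to all of the cited death hazard. Read as progression-free survival at 50% progression, the reported figure is too high by 1.5 to 13.2 points (50% against 48.5% to 36.8%). These figures rest on assumed progression rates, an assumed share of deaths before progression, independent hazards, and survival like that in the cited series.

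A reader might also infer that the trial's main conclusion is affected. It is not: the primary endpoint is 12-month local control per tumor, and neither its test nor its sample size uses these curves.

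**What to change.** In the SAP section on disease recurrence or progression and in Protocol 10.5.5, choose one quantity for each of the two outcomes and make the rule, estimator and label agree.

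- **If time to progression is meant**, as the outcome names suggest: report cumulative incidence (Aalen-Johansen) with death without prior progression as the competing event. Censor only patients last known alive and progression-free, and drop the progression-free survival label.
- **If progression-free survival is meant**: keep Kaplan-Meier and the label, and count death from any cause as an event.

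Changing the estimator without the label would not do. In the worked case, one minus the cumulative incidence is 54.9%, further from the progression-free survival of 36.8% than the planned 50%. Kaplan-Meier remains right for overall survival.

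The cost is rewording and a little more analysis work; deaths are already needed for overall survival and subject disposition. One limit should be stated in the report. Hospice entry is documented as early termination (Protocol 7.9), and other local treatment of an index tumor requires withdrawal (Protocol 7.8). Deaths after these exits may be incompletely captured, and either version would then miss some of them.

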6.2. Inclusion Criteria

Eligible patients for this study must meet all of the following criteria:

- 6.2.1. Patient must be at least 18 years old.
- 6.2.2. Patient has signed a written informed consent.
- 6.2.3. Patient presents with Stage 4 pulmonary metastatic disease with metastatic disease previously confirmed by prior biopsy;
or
Patient presents with Stage 4 pulmonary metastatic disease previously confirmed on imaging (e.g. CT) with histology proven primary cancer.
- 6.2.4. Patient has up to 6 local pulmonary metastases targetable by cryoablation.
- 6.2.5. Targeted index tumor(s) defined as intra pulmonary or pleural with a maximum size of 3.5 cm, measured in the longest cross sectional dimension.
- 6.2.6. The target index tumor(s) is determined (by CT images) to be in a location where cryoablation is technically achievable based on the proximity of adjacent organs/ structures and is greater than 0.5 cm from any critical organ/structure (possibly achieved with additional maneuvers such as iatrogenic pneumothorax or hydrodissection).
- 6.2.7. Karnofsky Performance Scale (KPS) score ≥ 60 .
- 6.2.8. Platelet count $>50,000/\text{mm}^3$ within 8 weeks prior to initial cryoablation procedure.
- 6.2.9. INR <1.5 within 8 weeks prior to initial cryoablation procedure.
- 6.2.10. Patient has a life expectancy of >3 months.

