8.4. Physical Performance

Physical function assessments will be measured using Karnofsky Performance Scale (KPS).

Karnofsky Performance Scale (KPS)

The Karnofsky Performance Scale is a standard way of measuring the ability of cancer patients to perform ordinary tasks. The scores range from 0 to 100. A higher score means the patient is better able to carry out daily activities. KPS may be used to determine a patient's prognosis, to measure changes in a patient's ability to function. (See Appendix D)

KPS will be assessed at screening and months 1, 3, 6, 12, 18, and 24.

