- **Time to overall cancer progression** is defined as the time in days from the first cryoablation procedure to cancer progression (i.e., any location of active cancer disease). Patients without cancer progression will be censored at the date of their last visit or their date of death (due to any cause). Overall cancer progression free survival rates will be summarized by using Kaplan-Meier methodology.
- **Time to untreatable metastatic lung disease control with cryoablation** is defined as the time in days from the first cryoablation procedure to the time when the metastatic lung disease cannot be treated with cryoablation. Overall time to untreatable metastatic lung disease progression rates will be summarized by using Kaplan-Meier methodology.
- **Time to untreatable metastatic lung disease control with focal therapy** is defined as the time in days from the first cryoablation procedure to the time when the metastatic lung disease cannot be treated by focal (e.g., ablation, surgery, SBRT) intervention for control of metastatic lung disease. Overall time to untreatable metastatic lung disease progression rates will be summarized by using Kaplan-Meier methodology.

Intra-procedural data

Initial cryoablation procedure information including the tumor size and number, cryoablation needle type and the number of each type of needle used, freeze and thaw times, procedure times, and anesthesia type.

Physical performance and quality of life

Physical performance (KPS) and quality of life (SF-12) assessments will be made by examining the change in the baseline scores to those reported post-operatively as defined in Sections 8.4 and 8.5, respectively.

Subset Analyses

Analysis may be done on outcomes for subgroups including, but not limited to, gender, primary cancer and tumor size.

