The primary efficacy endpoint for the trial is 12-month local control. The papers shown below were used as reference for clinicians who determined a clinically relevant efficacy endpoint performance goal was 84% success at 12-months. This observed cryoablation group's local control rate will be tested against this performance goal.

Paper	Lesions	12-month Local Control Success	Lower 97.5% 1-sided Wilson CI
Okuneiff (2006)	125	91%	0.8469
Rusthoven (2009)	63	100%	0.9425
Baschnagel (2013)	47	97%	0.8757
Ricardi (2012)	77	94%	0.8632
Norihisa (2008)	43	94.50%	0.8337
Yoon (2006)	101	90%	0.8261

This test is accomplished by testing against the following hypotheses:

$$H_0: C_{\text{DEVICE}} \leq 84.0\%$$

$$H_a: C_{\text{DEVICE}} > 84.0\%$$

where C_{DEVICE} is the observed cryoablation local control rate at 12-months.

The null hypothesis will be rejected and the primary efficacy endpoint performance goal will be met if the lower bound of the one-sided 97.5% confidence interval for the 12-month tumor local control rate is greater than 84.0%.

PASS 12 was used to calculate the sample size needed. A sample size of 203 lesions achieves 85% power (and guarantees at least 80% power) to detect a difference ($P_1 - P_0$) of 0.0700 using a one-sided binomial test. The target significance level is 0.0250. The actual significance level achieved by this test is 0.0239. These results assume that the population proportion under the null hypothesis is 0.8400.

Power Analysis of One Proportion

Numeric Results for testing $H_0: P = P_0$ versus $H_1: P > P_0$

Test Statistic: Exact Test

Power	N	Proportion		Target Alpha	Actual Alpha	Beta	Reject H_0 If $R \geq$ This
		Given H_0 (P_0)	Given H_1 (P_1)				
0.8501	203	0.8400	0.9100	0.0250	0.0239	0.1499	181

To account for up-to a 10% 12-month lesion attrition rate, the final sample size has been increased to 226 lesions.

Note that, for the purposes for sample size calculations, the observations are assumed to be independent. However, the primary analyses will account for within subject correlation, as described below.

General Analysis Methods

Data will be analyzed using descriptive statistics. Continuous variables (e.g., age) will be summarized by the number of patients, mean, standard deviation, median, interquartile range, minimum and maximum. Categorical variables (e.g., race) will be summarized by frequencies and percentages of patients in each category. 95% confidence intervals will be calculated as appropriate.

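### The only within-patient change summary the SAP names for KPS and SF-12 is percent change, whose mean tends upward when nothing has changed; paired change in points should replace it

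*SAP*

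**What the plan says.** Protocol 10.5.5 says that KPS and SF-12 "assessments will be made by examining the change in the baseline scores to those reported post-operatively as defined in Sections 8.4 and 8.5". It does not mention percent change.

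The SAP, under Physical performance and quality of life, opens in nearly the same terms: "assessments will be made by examining the change in the baseline scores to those reported post-operatively and at follow-up visits". It then names two outputs. The first is the scores themselves: "The KPS scale and each of the eight SF-12 domains will be summarized at each time point by descriptive statistics". The second is "Percent change from baseline for each measure will also be summarized by descriptive statistics". A tabulation of change in points is not named.

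The SAP's General Analysis Methods section defines the descriptive statistics for continuous variables as the number of patients, "mean, standard deviation, median, interquartile range, minimum and maximum", with 95% confidence intervals as appropriate. A mean percent change will therefore be reported, together with a median.

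For KPS, Protocol 8.4 states that "The scores range from 0 to 100", and inclusion criterion 6.2.7 requires "Karnofsky Performance Scale (KPS) score ≥ 60". For SF-12, Protocol 5.6, 8.5 and Appendix E give the domains and items but no scoring method. Neither document says how percent change is handled at a zero baseline.

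**The concern.** Percent change divides each patient's change by that patient's own baseline. The same gain in points counts for more from a low baseline than the same loss does from a high one. Averaged over patients, this pushes the mean upward even when scores are only fluctuating. The study has a single arm, so no control group shows the same artefact and lets a reader subtract it.

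Change in physical function and quality of life is a listed outcome in Protocol 5.3, and Protocol 5.8 names better performance status as a potential benefit. A small positive mean percent change in KPS or in an SF-12 domain could be read as modest benefit when the scores in points are flat or falling.

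A second, conditional problem is that percent change has no value when the baseline score is 0.

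**Working it through.** The documents state no KPS or SF-12 figure, so there is nothing to reproduce. Three checks were made.

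**1. Can the baseline be zero?**
- KPS: an eligible patient has at least 60 (Protocol 6.2.7), so no.
- SF-12: possible only if domains are scored 0 to 100, where the worst response scores 0. A norm-based score with positive values does not reach 0. Both scorings are assumptions.

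**2. Two patients swap scores *a* and *b*.** Mean change in points is [(b − a) + (a − b)]/2 = 0. Mean percent change is 100 × [(b − a)/a + (a − b)/b]/2 = 50 × (b − a)²/(ab), which is positive whenever a and b differ.

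| Scores swapped | Percent changes | Mean percent change | Mean change in points |
|---|---|---|---|
| KPS 80 and 90 | +12.5, −11.1 | +0.7% | 0 |
| KPS 60 and 80 | +33.3, −25.0 | +4.2% | 0 |
| KPS 60 and 100 | +66.7, −40.0 | +13.3% | 0 |
| SF-12 domain (0–100) 50 and 75 | +50.0, −33.3 | +8.3% | 0 |
| SF-12 domain (0–100) 25 and 50 | +100.0, −50.0 | +25.0% | 0 |

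The 25-point steps fit domains that Appendix E asks with one five-option item (general health, pain, energy, social activities), if these are scored 0 to 100.

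**3. Expected value when nothing changes on average.** Assume baseline X and follow-up Y have the same distribution. With probability ρ a patient keeps the baseline score; otherwise Y is an independent draw, so the correlation is ρ. Then

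mean percent change among non-zero baselines = 100 × (1 − ρ) × {E[Y] × E[1/X | X > 0] − 1}.

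*KPS, levels 60, 70, 80, 90, 100.*
- Proportions 0.05, 0.15, 0.25, 0.35, 0.20: E[Y] = 85 and E[1/X] = 0.01199, so the product is 1.0192. With ρ = 0.3, 0.7 × 1.92% = +1.34%; with ρ = 0.7, +0.57%.
- Equal proportions: 80 × 0.012913 = 1.0330. With ρ = 0.3, +2.31%; with ρ = 0.7, +0.99%.
- Range: +0.6% to +2.3%.

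*SF-12 domain scored 0, 25, 50, 75, 100.*
- Proportions 0.05, 0.10, 0.25, 0.30, 0.30: E[Y] = 67.5 and E[1/X | X > 0] = 0.016/0.95 = 0.016842, so the product is 1.1368. With ρ = 0.5, +6.84%. In the same patients the mean change in points is 0.5 × (67.5 − 67.5/0.95) = −1.8.
- Over three assumed distributions with 2% to 10% of patients at zero baseline, and ρ of 0.5 to 0.7: +3.7% to +7.8%, while the same patients' mean change is −0.5 to −3.0 points. With zero-baseline patients included, the mean change in points is 0.

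*Norm-based SF-12 score.* Assume mean 45, SD 10, values limited to 20 to 70. Simulation gives +2.8%, +1.7% and +1.1% at correlations 0.5, 0.7 and 0.8.

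**The case against.** The strongest reply is that percent change is an addition. The SAP paragraph opens with change in scores, in nearly the protocol's words, and summarises raw scores at every time point before percent change is mentioned. The median and interquartile range are also reported, so a reader could see a mean that disagrees with the scores. Nothing is tested on KPS or SF-12, and SF-12 is collected only at screening, month 1 and month 3.

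Much of this stands. A reader might infer that percent change is the SAP's only measure of change, or that the SAP contradicts the protocol. The text supports neither: the opening sentence can be read to include change in points. What it does not do is name that change as a table, and percent change is named.

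Visit-level scores do not fully replace a paired change. They describe whoever attended each visit. Patients have Stage 4 disease, the life-expectancy criterion is only more than 3 months (Protocol 6.2.10), and withdrawal and hospice entry are foreseen (Protocol 7.9). A difference between visit means can therefore mix change with attrition. Paired change in points avoids this among patients observed at both visits.

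Three further inferences also go too far:
- **Undefined values for KPS.** The entry criterion rules out a zero baseline. For SF-12 it depends on scoring that the documents do not give.
- **Dropped zero-baseline patients inflate the result.** A patient at the floor can only stay or improve, so losing that patient removes potential improvement. The harm is that the worst-off patients vanish from the summary.
- **An artefact of +25% should be expected.** That figure needs half the patients to double and half to halve, with nobody unchanged. The assumed distributions give far less.

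**Conclusion.** The point holds as a minor one. Percent change is the only within-patient change summary that the SAP explicitly specifies for KPS and SF-12, and its mean tends upward when there is no true change.

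The artefact is about +0.6% to +2.3% for KPS, +1.1% to +2.8% for a norm-based SF-12 score, and +3.7% to +7.8% for an SF-12 domain scored 0 to 100. These ranges rest on assumed score distributions and correlations. The direction was upward in every scenario tried; only the size varied. In the 0-to-100 scenarios the percent summary rises while the same patients' mean score falls.

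The zero-baseline gap applies to SF-12 only, and only under 0-to-100 scoring. The consequence is confined to descriptive supportive outcomes; the primary endpoint and its test are untouched.

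**What to change.** In the SAP section on physical performance and quality of life, replace percent change with the paired change in points from baseline, with mean and 95% CI at each visit where the measure is collected, for KPS and for each SF-12 domain. This makes explicit what Protocol 10.5.5 already asks for.

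State the SF-12 scoring method in the same place. If percent change is kept for any reason, give a rule for a zero baseline and report how many patients it affects.

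The cost is a sentence or two in the SAP and no extra data.
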